7.4.3.3 Long term follow-up (LTFU)

LTFU is survival follow up. After completion of the treatment and safety follow-up period, all the subjects will be followed for survival status. Subjects will be contacted by phone or in person every 12 weeks \pm 7 days after discontinuation to assess survival status until subject death or study termination. Survival and subsequent antitumor therapy will be collected during these calls/interviews.

7.5 Biological Samples

7.5.1 PK Samples

Blood samples will be collected from all the subjects for PK analysis.

• **Part A study:**

Table 11 PK Sample Time Points and Time Windows

Time for Blood Collection	Single Dosing Study			Multiple Dosing Study				
	Cycle 0 (4 Days)			Cycle 1 (28 Days)			Cycle 2 (28 days)	\geq Cycle 3 (28 days)
	D1	D2	D3	D1	D8	D15	D1	D1
-1h (prior to dosing)	X			X	X	X	X	X
0.5 h	X					X		
1 h	X					X		
2 h	X					X		
3 h	X					X		
4 h	X					X	X	X (\pm 2h)
6 h	X					X		
8 h	X					X		
10 h	X					X		
24 h	X	X	X			X (C1D16 pre-dose)		

• **Part B study:**

Time for Blood Collection	Multiple Dosing Study				
	Cycle 1 (28 Days)			Cycle 2 (28 days)	\geq Cycle 3 (28 days)
	C1D1	C1D8	C1D15	C2D1	C3D1
-1h (prior to dosing)	X	X	X	X	X
0.5 h	X		X		

1 h	X		X		
2 h	X		X	X	
3 h	X		X	X	
4 h	X		X	X	
6 h	X		X	X	
8 h	X		X		
10 h	X		X		
24 h	X (C1D2 pre-dose)		X (C1D16 pre-dose)		

• **Part C study:**

Time for Blood Collection	Multiple Dosing Study		
	Cycle 1 (28 Days)	Cycle 2 (28 days)	≥Cycle 3 (28 days)
	C1D1	C2D1	C3D1
-1h (prior to dosing)	X	X	X
0.5 h			
1 h			
2 h	X	X	
3 h	X	X	
4 h	X	X	X (± 2h)
6 h	X	X	
8 h	X	X	
10 h	X	X	
24 h	X (C1D2 pre-dose)	X (C2D2 pre-dose)	

Table 12 PK Samples Time Windows

Collection Time Point	Time window
D1 (prior to dosing)	Within 60 min
0~4 h after administration (4 h included)	±3 min
4~10 h after administration (10 h included)	±5 min
10~24 h after administration (24 h included)	±10 min
Greater than 24 after administration (24 h not included)	±30 min

7.5.2 Sample Preparation

Details of sample collection, processing, shipping and storage will be described in the separately Laboratory Manual.

Samples will be analyzed using a previously validated method, which will be described in the Laboratory Manual of the study site.

8 Lifestyle and/or Dietary Management

8.1 Pregnancy Precautions

8.1.1 Definition of Childbearing Potential

For the purposes of this study, a female born subject is considered of childbearing potential following the initiation of puberty until becoming post-menopausal, unless permanently sterile or ovarian failure with medical documentations.

Post-menopausal defined as no menses for at least 12 months after stopping all hormone treatments and with follicle stimulating hormone (FSH) level in the post-menopausal range (confirmed by lab test).

Permanent sterilization includes hysterectomy, bilateral oophorectomy, or bilateral salpingectomy in a female subject of any age.

A male born subject is considered fertile after the initiation of puberty unless permanently sterile by bilateral orchiectomy or medical documentation.

8.1.2 Contraception Requirements for Female Subjects of Childbearing Potential

Complete abstinence from intercourse of reproductive potential is an acceptable method of contraception only when it is in line with the subject's preferred and usual lifestyle.

Sexually active female subjects of childbearing potential must agree to use at least 1 highly effective contraception and 1 additional method at least 1 month prior to initiation of the study, during the study, and for 6 months after the last administration of the study drug. Female subjects must also refrain from egg donation and in vitro fertilization during the study and until at least 30 days after the last of study drug.

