6. Previous therapy failed or intolerable, or standard therapy not available:

Part A: Previous therapy failed or intolerable, or standard therapy not available.

Part B/C: Patients should have received at least 1 line ET, or received no more than 1-line systematic chemotherapy for advanced/metastatic disease, no more than 1 target therapy.

	
 7. Eastern Cooperative Oncology Group (ECOG) performance status of 0 or 1(See Appendix 6). 8. At least one measurable lesion according to RECISTv1.1 criteria. 9. Life expectancy \geq 12 weeks. 10. Adequate organ and bone marrow function (no use of hematopoietic stimulating factor, no blood transfusion or human albumin within 7 days prior to screening): 
 a) Blood routine: Absolute neutrophil count (ANC) \geq $1.5 \times 10^9/L$; Platelet count (PLT) \geq $100 \times 10^9/L$; Hemoglobin (HGB) \geq 90 g/L; b) Liver function: Serum Total bilirubin (TBIL) \leq 1.5 Upper limit of normal value (ULN); Alanine aminotransferase (ALT) and Aspartate transferase (AST) \leq 3\timesULN in subjects without liver metastasis; ALT or AST \leq 5\timesULN with liver metastasis; c) Renal function: Serum creatinine \leq 1.5\timesULN or estimated creatinine clearance (CLcr) \geq 60 mL/min as calculated using Cockcroft-Gault formula; d) Coagulation function: Activated Partial thromboplastin Time (APTT) and international normalized ratio (INR) \leq 1.5\timesULN (or within target range if on anticoagulation therapy); e) Cardiac function: Echocardiography (ECHO) shows left ventricular ejection fraction (LVEF) > 50%. 11. Women of childbearing potential must have a negative serum pregnancy test within 7 days prior to the first dose. Female patients of childbearing potential must agree to use effective methods of contraception from the time of signature of informed consent, throughout the study and for 6 months after the last dose of the investigational product, like double barrier methods, condoms, oral or injectable contraceptives, intrauterine devices, etc. All female subjects will be considered to be of childbearing potential unless they are postmenopausal, postmenopausal, or sterilized (hysterectomy, tubal resection).

Exclusion Criteria
	
 1. Documented medical history or ongoing gastrointestinal disease (Including difficulty in swallowing capsules, Crohn's disease,

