8. Eastern Cooperative Oncology Group (ECOG) performance status of 0 or 1.
9. At least one measurable lesion according to RECISTv1.1 criteria.
10. Life expectancy ≥ 12 weeks.
11. Adequate organ and bone marrow function (no use of hematopoietic stimulating factor, no blood transfusion or human albumin within 7 days prior to screening):
- Blood routine: Absolute neutrophil count (ANC) $\geq 1.5 \times 10^9/L$; Platelet count (PLT) $\geq 100 \times 10^9/L$; Hemoglobin (HGB) ≥ 90 g/L;
 - Liver function: Serum Total bilirubin (TBIL) ≤ 1.5 Upper limit of normal value (ULN); Alanine aminotransferase (ALT) and Aspartate transferase (AST) $\leq 3 \times ULN$ in subjects without liver metastasis; ALT or AST $\leq 5 \times ULN$ with liver metastasis;
 - Renal function: Serum creatinine $\leq 1.5 \times ULN$ or estimated creatinine clearance (CLcr) ≥ 60 mL/min as calculated using Cockcroft-Gault formula;
 - Coagulation function: Activated Partial thromboplastin Time (APTT) and international normalized ratio (INR) $\leq 1.5 \times ULN$ (or within target range if on anticoagulation therapy);
 - Cardiac function: Echocardiography (ECHO) shows left ventricular ejection fraction (LVEF) $> 50\%$.
12. Women of childbearing potential must have a negative serum pregnancy test within 7 days prior to the first dose. Female patients of childbearing potential must agree to use effective methods of contraception from the time of signature of informed consent, throughout the study and for 6 months after the last dose of the investigational product, like double barrier methods, condoms, oral or injectable contraceptives, intrauterine devices, etc. All female subjects will be considered to be of childbearing potential

unless they are postmenopausal, postmenopausal, or sterilized (hysterectomy, tubal resection).

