7.2 Study Start and End of Study Definitions

The start of the study is defined as the date the first subject, who is subsequently enrolled, signs an ICF. The point of enrolment occurs at the time of subject number allocation. The end of study is defined as the date of the last subject's last assessment.

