7.4.1 Screening Period (Day -28~Day -1) for All Subjects

After signing the ICF, a subject should undergo medical screening to assess whether he/she is eligible to participate in the study according to the inclusion criteria. The screening evaluation will be completed within 28 days prior to the first administration of the investigational drug.

Administrative Procedures:

- Informed Consent
- Inclusion/Exclusion Criteria
- Demographics
- Medical history
- Concurrent diseases

Clinical Procedures/Assessments:

- Weight
- Body height
- Physical examination
- vital signs

- ECOG Score
- 12-lead ECG
- Echocardiogram

Laboratory tests:

- Blood Chemistry
- Hematology
- Coagulation
- Urinalysis
- Virology: HBV, HCV, and HIV
- Pregnancy
- COVID-19

Efficacy Assessments:

- Tumor Assessment

Biomarker Exploration:

- ¹⁸F-FES PET/CT15

Other:

- Adverse events and concomitant medication;

The information above should be obtained from the source file. For test values outside the normal range (outliers), the investigator will assess whether to repeat the test.

The investigator will review patient's medical history at the time of screening period. The history includes all current active diseases and any other conditions deemed clinically significant by the investigator. The date of last prior anticancer therapy(s) and treatment response must be recorded. Pre-enrollment imaging data can be collected for the investigator's reference. A complete medication history within 28 days prior to the first administration of the study drug should be reported.

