8.1.3.1 Methods that are Considered Less Highly Effective

- Progestogen-only oral hormonal contraception, where inhibition of ovulation is not the primary mode of action.
- Male condom with or without spermicide
- Cap, diaphragm, or sponge with spermicide

Note: a combination of male condom with either cap, diaphragm or sponge with spermicide (double-barrier methods) are also considered acceptable, but not highly effective, birth control methods.

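### Inclusion criterion 12 accepts a lower contraception standard than section 8.1.2, with a different start time and no pointer to it

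*Protocol*

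**What the plan says.** The protocol sets contraception rules for women of childbearing potential in two places.

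- **Eligibility.** Criterion 12 in section 5.2 and criterion 11 in the synopsis share the same wording. Such a woman "must agree to use effective methods of contraception from the time of signature of informed consent", and the examples offered are "like double barrier methods, condoms, oral or injectable contraceptives, intrauterine devices, etc". The obligation runs through the study and for 6 months after the last dose.
- **Pregnancy precautions.** Section 8.1.2 says that sexually active women of childbearing potential "must agree to use at least 1 highly effective contraception and 1 additional method", beginning "at least 1 month prior to initiation of the study" and ending 6 months after the last dose. Abstinence is accepted if it is the subject's usual way of life.

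Section 8.1.3 defines highly effective as a failure rate below 1% per year under consistent and correct use, and lists the qualifying methods. Section 8.1.3.1 lists those that fall short. They include "Male condom with or without spermicide", and double-barrier combinations "are also considered acceptable, but not highly effective, birth control methods".

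On timing, section 7.2 states: "The start of the study is defined as the date the first subject, who is subsequently enrolled, signs an ICF".

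**The concern.** A site decides enrolment by checking the criteria in section 5.2. Those criteria give condoms and double barrier as examples of adequate contraception, while the protocol's own classification says that neither is highly effective. A woman can therefore be correctly enrolled under 5.2 and be out of line with 8.1.2 from her first day. Nothing in criterion 12 would alert the site, because it does not mention section 8.1. The omission is not the protocol's general style: inclusion criterion 3, for instance, sends the reader to Appendix 6.

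The start of the obligation is also stated in two ways, and the one in 8.1.2 cannot be applied to an individual woman as written.

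What is at stake is subject safety. Section 9.5.4 acknowledges that the risk of FWD1802 in pregnancy has not been evaluated, so the rule meant to prevent exposed pregnancies should read the same wherever a site meets it.

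**Working it through.** No statistical quantity is involved, so the check sets the texts side by side.

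**1. The two rules**

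| Element | Criterion 12 / synopsis 11 | Section 8.1.2 |
|---|---|---|
| Standard | Effective methods, with examples | At least one highly effective method |
| Second method | Not requested | Required |
| Abstinence | Not mentioned | Accepted if usual lifestyle |
| Start | Signing of consent | A month or more before study initiation |
| End | 6 months after last dose | 6 months after last dose |
| Refers to the other text | No | No |

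The end of the obligation agrees. The standard and the start do not.

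**2. The five named examples against sections 8.1.3 and 8.1.3.1**

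- Double barrier: not highly effective.
- Condoms: not highly effective.
- Oral contraceptives: highly effective only where they act by inhibiting ovulation.
- Injectable contraceptives: highly effective on the same condition.
- Intrauterine device: highly effective.

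So 2 of 5 examples fail the first half of the 8.1.2 rule. Any of the five used alone fails the second half.

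**3. Test cases for a sexually active woman of childbearing potential**

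- Condoms only: within the examples of criterion 12; fails 8.1.2.
- Double barrier only: within the examples of criterion 12; fails 8.1.2.
- Intrauterine device plus condom: meets both.

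The first two cases show the gap. The third shows that the rules can be met together.

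**4. What study initiation could mean in 8.1.2**

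- *The study start of section 7.2.* This is one calendar date for the whole trial, set by the first enrolled subject's consent. It gives no usable start for anyone enrolled later.
- *The subject's own consent.* Section 8.1.2 then begins a month before the point at which criterion 12 begins.
- *The subject's own first dose.* Whether starting at consent is early enough then depends on how long before the first dose she signs.

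None of these readings makes the 8.1.2 rule the same as the rule in criterion 12, and the protocol does not choose among them.

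**The case against.** The strongest reply is that the two texts are compatible. Criterion 12 gives an open-ended list and never says that a single method is enough. Section 8.1.2 is equally binding and supplies the detail, and a site that reads the whole protocol will apply the stricter rule. It is true that both can be satisfied at once, so a reader who inferred a flat contradiction would go too far. What remains is that the eligibility text names, as adequate, methods that the later section finds insufficient, and does not send the site there.

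A second reply is that few women are exposed. Pre- and perimenopausal women may enter only on an LHRH agonist, a negative serum pregnancy test is needed within 7 days before the first dose, and section 8.1.4 requires contraception counselling to be repeated. This stands, and it limits the importance of the point. It does not explain why the protocol should carry two standards for the women it does regulate.

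A reader might also infer a definite shortfall in days from section 7.4.1, which says: "The screening evaluation will be completed within 28 days prior to the first administration of the investigational drug". The documents do not support such a figure. It would need study initiation to mean first dose, a fixed length for a month, and contraception starting only at consent within the 28-day window. Section 7.1 requires consent before screening begins, so consent is not firmly tied to that window, and a woman already using contraception has no shortfall.

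**Conclusion.** The point holds as a minor inconsistency between two stated safety rules. Criterion 12 and synopsis criterion 11 allow entry on methods that section 8.1.3.1 classes as not highly effective, without a second method, while section 8.1.2 requires one highly effective method plus one more. The start times differ, and the one in 8.1.2 has no meaning for an individual subject.

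The conclusion on the standard rests on the protocol's own classification and needs no assumption. The practical consequence assumes a site that checks eligibility against 5.2 without consulting section 8.1. The number of women affected cannot be stated, because the protocol does not say how many of its roughly 99 patients will be of childbearing potential; it is likely to be small. Dose escalation, sample size and analysis are unaffected.

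How often pregnancy tests are scheduled during treatment is a separate matter. It neither strengthens this point nor would be changed by the fix.

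**What to change.** In inclusion criterion 12 and synopsis criterion 11, replace the list of examples with a reference to section 8.1: one highly effective method from 8.1.3 plus one additional method, or abstinence on the terms of 8.1.2.

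In both the criteria and 8.1.2, give one start time relative to the subject's own first dose (C0D1 in Part A, C1D1 in Parts B and C). Twenty-eight days before that dose would match the LHRH-agonist lead-in already required of pre- and perimenopausal women by inclusion criterion 5.

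This is a change of wording, with one practical cost. A woman not already using contraception may wait up to 28 days. Because screening assessments must also fall within 28 days before the first dose, a start at consent on Day -28 leaves no slack, and a delay could mean repeating some tests. For a woman who also has to start an LHRH agonist, the two waits can run together.

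Since the 8.1.3 list would become the eligibility standard, the clinical team should confirm it when making the edit, in particular the oestrogen-containing products in a population with ER+ disease.

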8.1.3.1 Methods that are Considered Less Highly Effective

- Progestogen-only oral hormonal contraception, where inhibition of ovulation is not the primary mode of action.
- Male condom with or without spermicide
- Cap, diaphragm, or sponge with spermicide

Note: a combination of male condom with either cap, diaphragm or sponge with spermicide (double-barrier methods) are also considered acceptable, but not highly effective, birth control methods.

8.1.4 Unacceptable Birth Control Methods

Birth control methods that are unacceptable include periodic abstinence (eg, calendar, ovulation, symptothermal, postovulation methods), withdrawal (coitus interruptus), spermicides only, and lactational amenorrhea method. Female condom and male condom should not be used together.

Counseling about contraception and behaviors associated with an increased risk of pregnancy must be repeated, and pregnancy testing will be conducted at specified times

8.2 Meals and Dietary Restrictions

FWD1802 (and palbociclib) is administered after meal (within 30 minutes) with approximately 240 ml water. The subjects should start the recommended meal 30 minutes before administration of the drug product. Other dietary restrictions are as follows:

- During each dosing session, subjects will abstain from ingesting caffeine or xanthine containing products (e.g., coffee, tea, cola drinks, and chocolate) for 24 hours prior to the start of dosing until collection of the final PK samples during each session.
- During each dosing session, subjects will abstain from alcohol for 24 hours prior to the start of dosing and during each session.
- Use of tobacco products is not allowed 3 months prior to the screening visit.
- Use of traditional Chinese medicines or herbal products is not allowed 2 weeks prior to and during the study.

8.3 Physical Activity

- Subjects will abstain from strenuous exercise for 48 hours prior to each blood collection for clinical laboratory tests. Subjects may participate in light recreational activities during studies (e.g., watching television, reading).
- Subjects will be advised to stay indoors to avoid ≥ 15 min extreme exposure to the sun or sunbathing.

9 Assessments of Adverse Events

9.1 Adverse Events

The investigator is responsible for the detection and documentation of events meeting the criteria and definition of an AE or SAE as provided in this clinical study protocol. During the study, when there is a safety evaluation, the investigator or site staff will be responsible for detecting AEs and SAEs, as detailed in this section of the protocol.

The following definitions of terms are guided by the International Conference on Harmonization and the US Code of Federal Regulations and are included here verbatim. The terms “serious adverse event” and “adverse event” are commonly used by the Sponsor.

9.1.1 Adverse Event Definition

An AE is any untoward medical occurrence in a subject or clinical investigation participant administered a pharmaceutical product and which does not necessarily have a causal relationship with this treatment. An AE can therefore be any unfavorable and unintended sign (including an abnormal laboratory finding), symptom, or disease temporally associated with the use of a medicinal (investigational) product, whether or not related to the medicinal (investigational) product.

Examples of an AE include:

- Significant or unexpected worsening or exacerbation of the condition/indication under study.
- Exacerbation of a chronic or intermittent pre-existing condition including either an increase in frequency and/or intensity (grade) of the condition.
- New conditions detected or diagnosed after investigational product administration even though may have been present prior to the start of the study.
- Signs, symptoms, or the clinical sequelae associated with a suspected interaction of the investigational product with a concomitant medication.

9.1.2 Serious Adverse Event Definition

Any untoward medical occurrence that at any dose:

- Results in death,
- Is life-threatening-

Note: The term ‘life-threatening’ in the definition of ‘serious’ refers to any adverse drug experience (AE) that places the subject or participant, in the view of the investigator, at immediate risk of death from the reaction as it occurred, i.e., it does not include a reaction that, had it occurred in a more severe form, might have caused death.

- Requires in subject hospitalization or prolongation of existing hospitalization

Note: In general, hospitalization signifies that the subject or participant has been detained (usually involving at least an overnight stay) at the hospital or emergency ward for observation and/or treatment that would not have been appropriate in the physician's office or outpatient setting. Complications that occur during hospitalization are AEs. If a complication prolongs hospitalization or fulfills any other serious criteria, the event is serious. When in doubt as to whether "hospitalization" occurred or was necessary, the AE should be considered serious. Hospitalization for elective treatment of a pre-existing condition that did not worsen from baseline is not considered an AE.

- Results in persistent or significant disability/incapacity

Note: The term disability means a substantial disruption of a person's ability to conduct normal life functions.

- Is a congenital abnormality/birth defect.
- Important medical events that may not result in death, be life-threatening, or require hospitalization may be considered a serious adverse drug experience when, based upon appropriate medical judgment, they may jeopardize the subject or participant and may require medical or surgical intervention to prevent one of the outcomes listed in the above definition.

